However, the cost of the necessary equipment is relevant; the purchase cost is about 1.7 million euros, while the annual maintenance represents about 10% of this sum. In addition, we have to add the costs

for disposable material and equipment with limited reusability (usually ten procedures). Consequently, the cost of this technology is high and volume dependent [4]. The European Society of Medical Oncology (EMSO) also highlights the fact that the robotic approach can be more expensive than the commonly used VATS [22]. On the other hand, in the robotic approach other costs are reduced, such as those related to hospitalization, the occupation of intensive care units, and the treatment of complications, which are reduced. Furthermore, there are potential advantages such as reduction of blood loss and tissue trauma, and less need for surgery conversion to open surgery compared to VATS. Furthermore, from the patient's point of view, there is an improvement in the quality of life (less pain, faster healing with consequent rapid return to work, less burden on caregivers). Lastly, this method has the advantage of improving ergonomics and reduce the physical effort of the surgeon [23]. Previous studies have attempted to evaluate the cost-effectiveness profile of this method in the thoracic area. Camberlin's study [4] is an HTA report carried out by the Belgian agency KCE, whose economic evaluation consists of a literature review for cost evaluation and a budget impact analysis. This study highlights that the cost structure of the different surgical approaches is very different and difficult to compare and the studies are generally of low quality. However, the analysis of the studies points out that robotic surgery is more expensive than traditional approaches such as thoracotomy and VATS. The systematic review by Turchetti [24] draws the same conclusion, while focusing on further relevant aspects: the facilitation in the execution of complex and advanced operations and the different role of the assistant surgeon during robot-assisted thoracoscopy operations. The organizational aspect most addressed in the literature was instead the training course for the use of the robotic surgical platform [19].

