
Definition of efficacy outcomes

Efficacy and safety will be evaluated starting from the diagnosis and procedure fields of the SDO, from the life status derived from the ATS patient registry (NAR – Nuova Anagrafe Regionale) and from the data provided by the centers in terms of:

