3.3.2.2. Safety

- 30-day mortality
- Reoperation during hospitalization
- Need for conversion to thoracotomy for VATS and robotic surgery
- Major complications by type of surgery (Table 3)

Secondly, differences in terms of duration of operation and hospitalization will be evaluated. This information will be used for the cost-effectiveness assessment.

 Table 3 Complications of interest and related ICD-9-CM codes

COMPLICATION	CODE
Iatrogenic cerebrovascular infarction or hemorrhage	997.02
Central nervous system complication (Brain anoxic damage, Cerebral hypoxia)	997.01
Cardiac complications, not elsewhere classified	997.1
(Cardiac: arrest, insufficiency, cardiorespiratory insufficiency, heart failure)	
Post traumatic pulmonary insufficiency	518.5
Urinary complications, not elsewhere classified (Renal: Acute defaillance, acute failure, acute tubular necrosis specified as due to interventions)	997.5
Postoperative infection, not elsewhere classified	998.5x
Hemorrhage or hematoma or seroma complicating a procedure, not elsewhere classified	998.1x
Persistent postoperative fistula	998.6

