3.3.3. Collected variables

3.3.3.1. From administrative databases

The staff of the Epidemiology Unit involved in the study will extract the information specified in Table 4 from the current administrative databases of the ATS of Milan. Subsequently, it will perform the deterministic record linkage on a unique key (fiscal code) and will anonymize the dataset for the analysis, removing the tax code, deleting the dates once the time intervals necessary for the analysis have been calculated (age, length of hospitalization, length of post-operative stay, etc.), and assigning a random ID to the patient. Separate copy of correspondence between social security number and random id will be kept in a separate password protected file.

Data flow	Data relating to	Variables
Hospital Discharge	Patient	Civil status, study level
Summary (SDO)	Hospital admission	Admission date, intervention date, discharge date, type of discharge, within hospital transfers
	Diagnoses and complications	All ICD-9-CM diagnosis codes present in a SDO
	Procedures	DRGs, ICD-9-CM procedure codes, procedure date
Patient registry	Patient	Sex, birth date, city of residence, vital status at 2022/12/31
SDO, outpatient services, pharmaceuticals, exemptions	Patient comorbidities	Charlson comorbidity index calculated through the algorithm in use at the Epidemiology Unit
Cancer registry	Cancer	Histology (morphological code ICDO3, margins of resection, number of mediastinal lymph nodes removed, number of positive mediastinal lymph nodes, stage at diagnosis)

Table 4 Variables collected from administrative databases

3.3.3.2. From the data provided by the centers through a dedicated platform made available by the ATS of Milan

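### Table 3, which defines major complications for both data sources, names no pneumonia, atelectasis or prolonged air leak, so the safety comparison may be incomplete for respiratory morbidity

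*Combined protocol and SAP*

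**What the plan says.** Section 3.3.2.2 (Safety) lists four outcomes: 30-day mortality, in-hospital reoperation, conversion to thoracotomy, and "Major complications by type of surgery (Table 3"). Table 3 is titled "Complications of interest and related ICD-9-CM codes" and has eight rows:

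- 997.02, cerebrovascular
- 997.01, other central nervous system
- 997.1, cardiac, with cardiorespiratory insufficiency among its examples
- 518.5, "Post traumatic pulmonary insufficiency"
- 997.5, urinary and renal
- 998.5x, "Postoperative infection, not elsewhere classified"
- 998.1x, haemorrhage, haematoma or seroma
- 998.6, "Persistent postoperative fistula"

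The outcome definitions in 3.3.2 name the sources: "Efficacy and safety will be evaluated starting from the diagnosis and procedure fields of the SDO", together with the patient registry and data from the centres. In Table 5 (3.3.3.2), the entry for the centres' complications simply refers to Table 3. Table 4 (3.3.3.1) takes a wider extract from the discharge records: "All ICD-9-CM diagnosis codes present in a SDO".

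Section 3.3.4.2 expects major complications to be rare and will consider an inverse-probability-weighted (IPW) zero-inflated count model for them. No complication rate appears anywhere in the plan.

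**The concern.** Every patient in the study has a lung resection (Table 1). That pneumonia, atelectasis and prolonged air leak can follow such surgery is ordinary clinical knowledge, yet the table that defines the complication outcome names none of them. The centres' data do not fill the gap, because they are tied to the same table.

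What is at stake is the safety comparison of robotic surgery, VATS and thoracotomy. The introduction expects the robotic approach to lower some costs, "such as those related to hospitalization, the occupation of intensive care units, and the treatment of complications, which are reduced". An outcome that may leave out part of the respiratory events is a weak test of whether complications do fall. It is also open to inconsistent classification: one centre may enter an air leak under fistula while another enters nothing.

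**Working it through.** The plan states no figure on this point, so there is none to reproduce. The check is a reading of Table 3 against Tables 4 and 5, followed by an illustration on assumed rates.

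**Row count**

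- Rows naming pneumonia, atelectasis or prolonged air leak: 0 of 8.
- Rows with explicitly respiratory content: 518.5, and part of 997.1.
- Rows that might take in some of the three events: 998.5x (infection) and 998.6 (fistula). The infection row covers only infections not classified elsewhere, which suggests that a condition with its own code falls outside it. The fistula row gives no site and requires persistence. No row plausibly covers atelectasis.

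**Sources side by side**

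| Source | Data collected | Used in the outcome |
|---|---|---|
| Discharge records (Table 4) | all diagnosis codes | Table 3 codes |
| Centres (Table 5) | Table 3 items | Table 3 items |

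The discharge data could support a respiratory group, but the outcome definition does not use them for one. An event outside Table 3 contributes nothing, whether the outcome is a count or any-versus-none.

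**Possible effect on the odds ratio (all rates assumed)**

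Let Table 3 capture complications in 6% of each group, and let uncaptured respiratory events occur independently with probability u. The full rate is 1 − 0.94 × (1 − u).

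- u = 10%: 1 − 0.94 × 0.90 = 15.4%
- u = 5%: 1 − 0.94 × 0.95 = 10.7%

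Table 3 alone gives an odds ratio (robotic versus open) of 1.00 in every case. With all events counted:

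| u open | u robotic | Full rates, open and robotic | Odds ratio |
|---|---|---|---|
| 10% | 5% | 15.4%, 10.7% | (0.107/0.893) / (0.154/0.846) = 0.66 |
| 10% | 10% | 15.4%, 15.4% | 1.00 |
| 5% | 10% | 10.7%, 15.4% | 1/0.658 = 1.52 |

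The result can go either way, depending entirely on u.

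**Share of patients with a complication who are missed**

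- u = 10%: (15.4 − 6)/15.4 = 61%
- u = 5%: (10.7 − 6)/10.7 = 44%
- The share exceeds one half only when the full rate is above 12%, that is when u > 1 − 0.88/0.94 = 6.4%.

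**Possible effect on power (assumed rates)**

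Section 3.3.4.1 gives n = 5400 and a robotic share of 0.12, hence 0.12 × 5400 = 648 robotic patients and 4752 others. Assume a risk ratio of 0.75 for all events, a two-sided 0.05 test of two proportions, and no weighting.

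| Full rate, others | 30% captured | 50% | 70% | 100% |
|---|---|---|---|---|
| 20% | 0.32 | 0.53 | 0.70 | 0.88 |
| 30% | 0.48 | 0.74 | 0.90 | 0.98 |

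Narrow capture would cost power. None of this shows what the actual capture is.

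**The case against.** The outcome is labelled major complications and expected to be rare, so a short list is defensible, and neither atelectasis nor an air leak is automatically major. Most Table 3 rows are worded as consequences of a procedure. General pneumonia or atelectasis codes need not be, and Table 4 lists no present-on-admission indicator, so a broader main outcome could gain misclassification along with events. These arguments stand. They are why the present outcome should be kept and the respiratory group shown beside it.

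The infection and fistula rows may already take in some pneumonias and air leaks. That is possible, but the plan does not say so, and it leaves atelectasis without a row. The detailed centre form is in Annex 2, which is not in the text reviewed, and some centre data come from existing registries and records. Extra fields there may help, but they would not enter an outcome that 3.3.2.2 ties to Table 3.

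A reader might infer that the outcome misses most respiratory morbidity. The documents do not support that: they give no rates, pulmonary insufficiency is listed, and two further rows may overlap. A reader might also infer that complication costs are understated by more than half, or that the decision tree will be wrong. This does not follow either. Length of stay feeds the cost-effectiveness assessment (3.3.2.2), and resource use is measured from administrative data (3.4.3), both independently of Table 3. Section 3.4.3 specifies no complication branch and allows further inputs to be calculated from the cohort. A shortfall in counted patients is not a shortfall in cost, and even the count shortfall is only 44% in the 5% illustration above.

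**Conclusion.** The gap is real but limited. Both sources use one list that names none of the three events, and a patient who has one of them without a Table 3 code is counted as complication-free. The safety comparison may therefore be incomplete for respiratory morbidity. Its size and direction cannot be derived from the documents: the odds ratios of 0.66 to 1.52 and the power figures above rest wholly on assumed rates. The conclusion assumes that the analysis follows Table 3 as printed and that Annex 2 adds nothing to the outcome. It is a low-cost improvement to a secondary part of the plan and does not undermine the survival or cost analyses.

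**What to change.** 1. Keep the present Table 3 outcome unchanged.
2. Pre-specify a respiratory group: postoperative pneumonia, atelectasis or other postoperative respiratory complication, and prolonged air leak. Define it with the surgeons from the diagnosis codes that Table 4 already extracts, preferring codes specific to postoperative events.
3. Report this group separately by approach with the same IPW analysis, and show Table 3 plus the respiratory group as a supporting analysis.
4. State which events the infection (998.5x) and fistula (998.6) rows are meant to cover, so that centres classify alike.
5. Add matching items to the centre form where registry or record data already hold them, before the pilot on two patients per centre.

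Cost: on the discharge side, a longer code list and no new extraction. On the centre side, a little more entry, which matters because about 5,000 patients are retrospective and participation is voluntary and unfunded (section 6); hence the restriction to data already held. Some added codes may reflect disease present before surgery. Reporting the group separately keeps that problem visible and out of the Table 3 outcome.

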3.3.3. Collected variables

3.3.3.1. From administrative databases

The staff of the Epidemiology Unit involved in the study will extract the information specified in Table 4 from the current administrative databases of the ATS of Milan. Subsequently, it will perform the deterministic record linkage on a unique key (fiscal code) and will anonymize the dataset for the analysis, removing the tax code, deleting the dates once the time intervals necessary for the analysis have been calculated (age, length of hospitalization, length of post-operative stay, etc.), and assigning a random ID to the patient. Separate copy of correspondence between social security number and random id will be kept in a separate password protected file.

Data flow	Data relating to	Variables
Hospital Discharge	Patient	Civil status, study level
Summary (SDO)	Hospital admission	Admission date, intervention date, discharge date, type of discharge, within hospital transfers
	Diagnoses and complications	All ICD-9-CM diagnosis codes present in a SDO
	Procedures	DRGs, ICD-9-CM procedure codes, procedure date
Patient registry	Patient	Sex, birth date, city of residence, vital status at 2022/12/31
SDO, outpatient services, pharmaceuticals, exemptions	Patient comorbidities	Charlson comorbidity index calculated through the algorithm in use at the Epidemiology Unit
Cancer registry	Cancer	Histology (morphological code ICDO3, margins of resection, number of mediastinal lymph nodes removed, number of positive mediastinal lymph nodes, stage at diagnosis)

Table 4 Variables collected from administrative databases

3.3.3.2. From the data provided by the centers through a dedicated platform made available by the ATS of Milan

The Epidemiology Unit of the ATS of Milan has an IT platform, which can display the list of their patients included in the study only to clinicians who have or have had the patient in treatment. The same platform allows the clinicians in charge to view the information relating to the patient and pertinent to the study in question. Information can be derived from the administrative databases and from the internal databases of the center. The platform will also allow to fill in an ad hoc questionnaire, which will be piloted on 2 patients per center, for the collection of additional data necessary for the study. The information collected will form a database that will be linked via fiscal code to that derived from administrative flows passing through the third table of correspondence between random id and fiscal code. The questionnaire will collect the following information (details in the data collection form, Annex 2). Part of the information necessary for the study will be acquired by the Epidemiology Unit of the ATS of Milan directly from available internal information flows of the participating Centers. Specifically, this is information collected by the participating Centers in the context of collaboration with important projects for the construction of European and Italian registries (such as those of the ESTS (European Society of Thoracic Surgeons) and the Study Group and Italian Register of VATS Lobectomy) or which can be extracted by participating centers from computerized medical records. The participating centers will select the subjects included in this study and the variables included in the CRF of the same.

Data relating to:	Variables
Intervention	Surgical approach - Open - VATS
	 Need for conversion to thoracotomy

Table 5 Variables collected at participating thoracic surgery centers

Patient	 Equipment used (brand and model) Computer-assisted Need for conversion to thoracotomy Equipment used (brand and model) Smoking habit Performance status
Complications	See Table 3

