3.3.2. Prospective study design for the evaluation of quality of life and efficacy

All subjects who will undergo lung surgery (Table 1) during 2022 at the participating centers and will give their consent to participate in the study by signing the informed consent form at the prehospitalization or at hospitalization before surgery will be eligible to be enrolled. To evaluate the quality of life PROMs related, we will use the generic questionnaire EuroQol-5 Dimension (EQ-5D-5L) and the specific European Organization for Research and Treatment of Cancer Quality of Life Questionnaire-Lung Cancer (EORCT QLQ-LC29), which are available and validated in Italian [33,34]. The pre-intervention questionnaire will be completed on paper during hospitalization before the intervention or at pre-admission and the data will be entered into the web application of the ATS of Milan by dedicated staff. The subsequent questionnaires at day 7 and 30 can be self-completed by patients or electronically, using the dedicated web application of the ATS of Milan or in paper form, by filling in the documents issued on discharge for this purpose. At the first follow-up visit after 30 days, the patient will deliver the completed forms to the Thoracic Surgery department in charge of him. The Thoracic Surgery Department will forward all the documents, including pre-intervention documents, in a single mailing at the end of the study, to the Epidemiology Unit of ATS of Milan. The latter will enter the data and prepare it for subsequent analyses. The choice of how to complete the questionnaire will be left to the participating center. In both cases, when completing the first questionnaire, the study staff will enter the patient's fiscal code (patient identifier) in the application and a unique random ID will be generated which will be issued to the patient on paper so that he can enter it in the two subsequent self-compiled questionnaires. The information necessary for the evaluation of efficacy will be collected with the same modalities of the retrospective study. In addition to the evaluation of the quality of life, a questionnaire for the collection of patient experience (PREMs) will also be administered 30 days after the intervention or at the first follow-up visit [35,36]. The PREMs questionnaire will also be self-completed by patients either electronically, using the dedicated web application of the ATS of Milan, or in paper form, by filling in the document issued during hospitalization, the transmission of which to the Epidemiology Unit will take place with the methods indicated above.

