3.3.4. Data analysis

3.3.4.1. Power of the study

To study the efficacy, data from the retrospective and prospective study will be analyzed jointly. For the retrospective part, approximately 5,000 patients operated on for lung cancer in the participating centers from 01/01/2016 to 12/31/2021 will be included. Based on the average of approximately 450 subjects operated on in the participating centers over 6 months during the years 2019-2021, a sample of 400 subjects eligible for enrollment in 6 months during 2022 was considered in the prospective observational study. As regards the statistical power in the analysis of the primary efficacy outcome, i.e. long-term survival, the calculation was based on an assumption of non-inferiority. The following formula was used to calculate potency in survival studies which is based on the hazard ratio [37].

$$1-\beta=\Phi(z-z_{1-\alpha}), z=(\ln(\theta)-\ln(\theta_0))\sqrt{np_Ap_Bp_E}$$

Where:

- θ_0 = hazard ratio under the null hypothesis, set equal to 1
- θ = observed hazard ratio
- pE = probability of event, i.e. death, set equal to 0.8 on the basis of epidemiological data from the ATS cancer registry
- pA = proportion of treated by robotic surgery equal to 0.12 on the basis of the data present in the SDOs for the year 2019 and of the preliminary information provided by the participating centers

pB = 1-pA

- n = sample size, equal to 5400
- Φ = distribution function of the standard normal
- A = I-type error, set equal to 0
- $1-\beta =$ statistical power

By varying the observed HR of VATS death versus the observed control group between 1.08 and 1.15, the statistical power ranged from 0.5 to 0.91. The power calculation was performed using R (v4.1.2, R Core Team 2021, Vienna, Austria.)

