3.3.4.2. Efficacy study

Since this is an observational study, all analyses must take confounding into account. For each outcome, a Direct Acyclic Graph (DAG) will be prepared, discussed by surgeons and epidemiologists, i.e. a graph that allows hypothesizing the causal relationship between intervention and outcome taking into account potential confounding factors, measurable or not. On the basis of this graph, which underlies a causal model, the variables to be included in the multinomial regression model will be selected for estimating the probability of being treated with each surgical modality as a function of potential confounders (known as propensity score). Among the variables that will be considered to define the DAGs are age, gender, performance status, treatment center and tumor characteristics. The inverse of this estimated probability will be used as weight in the regression models (inverse probability weighted, IPW) which will have the outcome as the dependent variable and the treatment modality as the independent variable: robotics, VATS and thoracotomy (reference). Differences in the duration of surgery and hospitalization will be analysed using an IPW generalized linear regression model. The 30-day odds ratio (OR) of death for VATS and robotic surgery versus thoracotomy will be estimated by means of an IPW logistic regression model. Relative survival will be evaluated using a Cox IPW model and expressed both in terms of hazard ratio (HR) and as one and 5 year survival. For inpatient reoperation, the need for conversion to thoracotomy for VATS vs. robotic surgery and major complications by type of surgery, which are expected to be rare events, a we will consider a IPW zero-inflated (Poisson or negative binomial) approach. All estimates will be presented together with 95% confidence intervals obtained from a robust standard error [39]. The same analyses, if allowed by the study number, will be repeated in the three surgical subgroups (atypical and segmental resection, lobectomy, pneumonectomy), in subjects aged less than or equal to 65 years vs. superior, in patients with performance status of 0 vs. 1 vs. 2. Sensitivity analyses will be carried out using alternative models for the probability of estimating the type of intervention.

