3.4.3. Model, clinical and cost input parameters

A decision tree model will be applied to summarize the consequences of the different interventions with regards to their clinical outcomes and costs incurred.

The input parameters for efficacy will be derived from the retrospective and prospective observational study. If further information becomes necessary, once the decision tree has been built, it will be calculated if possible by the court of the efficacy study. Otherwise, it will be derived from the literature. For the calculation of the QALYs, the utility values will be obtained starting from the results of the EQ-5D questionnaires prospectively administered to the patients, as described in paragraph 3.3.2., using the score function of van Hout et al. [41] and the Italian values of reference by Scalone et al [42].

For the input parameters of the costs, the identification of the resources will take place through a panel of expert thoracic surgeons and epidemiologists participating in the study. The quantification of resource consumption will take place using the administrative databases of the ATS with regard to pre-operative examinations, length of stay, follow-up visits, drugs and other identified direct health costs, using the same court identified for the efficacy study. To estimate the indirect health costs (patient travel, domestic assistance) the distance between the residence and the intervention hospital will be calculated for each patient. We will also use the estimate of the accesses number to the healthcare facility by surgical modality in the 30 days preceding and in the 6 months following the operation, using the administrative databases. For direct and indirect non-healthcare costs, such as the patient's lost days of work and lost productivity or early retirement, the *human capital approach* will be used.

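### Registry vital status is read on 31 December 2022 although surgery is allowed throughout 2022, so 30-day mortality may be incompletely observed for operations after 1 December (minor)

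*Combined protocol and SAP*

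**What the plan says.** - **Vital status.** Table 4 in section 3.3.3.1 lists the registry variables as "Sex, birth date, city of residence, vital status at 2022/12/31". Section 3.3.3.3 links the prospective patients to the same Table 4 variables.
- **Prospective enrolment.** Section 3.3.2 makes eligible, subject to consent, "All subjects who will undergo lung surgery (Table 1) during 2022 at the participating centers". Section 3.3.4.1 adds that "a sample of 400 subjects eligible for enrollment in 6 months during 2022 was considered". Neither section says which months.
- **Retrospective part.** Section 3.3.4.1: "approximately 5,000 patients operated on for lung cancer in the participating centers from 01/01/2016 to 12/31/2021 will be included".
- **Pooling.** Section 3.3.4.1: "To study the efficacy, data from the retrospective and prospective study will be analyzed jointly".
- **Endpoint and model.** Section 3.3.2.2 lists "30-day mortality" as a safety outcome. Under section 3.3.4.2, its odds ratios for VATS and robotic surgery against thoracotomy "will be estimated by means of an IPW logistic regression model".
- **Other sources.** The outcome definitions in section 3.3.2 also allow discharge-record (SDO) fields and data from the centres. Table 4 includes the type of discharge. Table 5 (section 3.3.3.2) lists no vital status, and the complications in Table 3 include no entry for death.

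No section says how to treat a patient with fewer than 30 days between surgery and the vital-status date.

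**The concern.** A 30-day yes/no outcome is known only if the patient died inside the window or was observed to its end. The plan fixes the date on which registry vital status is read, but it leaves open the date of the last prospective operation, which could be the same day. A patient operated on 20 December would have 11 days of registry follow-up; a death at home on day 15 would fall after the reading.

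The Cox model planned for long-term survival can censor such a patient, but the logistic model needs a yes or a no. With no rule stated, an obvious default is to code anyone without a recorded death as alive at 30 days. That would under-count early deaths in the most recent operations. The loss would be small in the pooled data and more visible in any prospective-only summary.

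**Working it through.** **Plan's own figures.** The plan gives no rate, power or precision for 30-day mortality. The nearest stated figure is the survival power in section 3.3.4.1, 0.5 to 0.91 for hazard ratios of 1.08 to 1.15. With n = 5,400, pA = 0.12, pB = 0.88 and pE = 0.8, √(5,400 × 0.12 × 0.88 × 0.8) = 21.36. At one-sided 5%, Φ(ln 1.08 × 21.36 − 1.645) = 0.50 and Φ(ln 1.15 × 21.36 − 1.645) = 0.91. The figure reproduces and does not depend on the point raised here.

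**Boundary date.** 31 December 2022 minus 30 days is 1 December 2022. An operation on 1 December has exactly 30 days. Operations from 2 to 31 December have f = 29 down to 0 days.

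**Who can be affected.** The roughly 5,000 retrospective patients were operated on by 31 December 2021 and have at least a year to the reading. Only the prospective 400 can be affected.

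**Number affected**, assuming even accrual: (N ÷ accrual days) × 30.

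| Reading of the enrolment period | Calculation | Affected | Share of pooled total |
|---|---|---|---|
| Six months ending by 1 December | – | 0 | 0 |
| 400 over July–December (184 days) | 400/184 × 30 | 65 | 65/5,400 = 1.2% |
| 400 over all of 2022 | 400/365 × 30 | 33 | 33/5,400 = 0.6% |
| 900 over all of 2022 (450 per six months) | 900/365 × 30 | 74 | 74/5,900 = 1.25% |

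In the July–December case, 65 is 16% of the prospective 400.

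**Deaths missed**, if every affected patient without a recorded death were coded as a survivor and deaths were spread evenly over the 30 days: (N ÷ days) × p × Σ(1 − f/30), f = 0 to 29. The sum is 15.5. The 30-day mortality p is not in the documents; 1% to 5% is assumed. For July–December:

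| Assumed p | Missed | Expected among 5,400 | Pooled risk read as | Prospective-only risk read as |
|---|---|---|---|---|
| 1% | 400/184 × 0.01 × 15.5 = 0.34 | 54 | 0.99% | 0.92% |
| 2% | 0.67 | 108 | 1.99% | 1.83% |
| 5% | 1.68 | 270 | 4.97% | 4.58% |

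The relative loss is 0.34/54 = 0.6% of pooled deaths and 0.34/4 = 8.4% of prospective deaths. Neither percentage depends on p.

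**The case against.** **Nobody may be operated on after 1 December.** Enrolment is planned for six months, and a window closing by that date leaves nothing to correct. This stands, and it makes the point conditional. The months are not stated, however, so the plan does not rule the problem out.

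**No text says such patients are coded as survivors.** This is also correct. They might be excluded or resolved from another source. The discharge record shows an in-hospital death and carries no stated cut-off. Prospective patients are expected at a visit after 30 days, which for a December operation falls in January. These sources narrow the gap without closing it. Type of discharge covers only deaths before discharge. The visit is described as the occasion for returning forms, and non-attendance does not establish death. No rule ties either source to this endpoint, so post-discharge deaths between 31 December and day 30 have no assigned source.

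**Two stronger readings are tempting but unsupported.**

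- A reader might infer that the loss favours robotic surgery because its share is growing. The plan projects the same share in both parts: 48/400 = 12% prospectively and 0.12 overall. At an assumed 2% mortality, missed robotic deaths would be about 0.67 × 0.12 = 0.08, against 5,400 × 0.12 × 0.02 = 13 expected.
- A reader might infer that the same date truncates the economic window "in the 30 days preceding and in the 6 months following the operation" in section 3.4.3. That window counts healthcare contacts from administrative flows, for which no end date is given. The 31 December date is attached only to registry vital status.

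**Conclusion.** The point holds as a minor, conditional gap. The vital-status date and the permitted surgery dates are not reconciled for a binary 30-day endpoint, and no rule covers incomplete windows. Under the planned 400 and the least favourable six months, about 65 patients are affected and about 0.3 to 1.7 deaths could be missed, under 1% of pooled 30-day deaths. If enrolment closes by 1 December 2022, the effect is nil.

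These sizes assume even accrual, deaths spread evenly over 30 days, a 30-day mortality of 1% to 5%, and coding of unresolved patients as survivors. Earlier clustering of deaths would make the loss smaller. The retrospective patients and the planned long-term survival power are not affected. The documents do not show that late patients will be miscoded, nor any direction of bias between approaches. The reason to act is that the ambiguity concerns a safety outcome and is cheap to remove.

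**What to change.** State the first and last dates of prospective enrolment in section 3.3.2, and set the Table 4 vital-status date at least 30 days after the last eligible operation. An operation on 31 December 2022 reaches day 30 on 30 January 2023, so 31 January 2023 suffices for any 2022 operation. The cost is one changed date and an extraction about one month later.

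If the date cannot move, add to section 3.3.4.2 that the 30-day mortality model includes only operations on or before 1 December 2022. At the planned 400 this loses at most about 65 patients, from that model alone.

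Either rule should be settled before the dataset is built, because section 3.3.3.1 deletes the dates once the time intervals have been calculated.
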